**Table 16-1: Schedule of study procedures for SP848 (Year 1)**

Study SP848	Year 1												Safety Follow-Up	
	V1 b	TC c	V2	V3	V4	V5	V6	V7	V8	V9	ETV d	Unsch Visit e	Final Visit f	
Visita														
Weeks in study	0		4	8	12	20	28	36	44	52				
Informed Consent	X													
Inclusion/exclusion criteria	X													
Medical history update	X													
Concomitant medications	X h	X	X	X	X	X	X	X	X	X	X	X	X	
Concomitant AEDs	X h	X	X	X	X	X	X	X	X	X	X	X	X	
Physical exam (complete)	X h				X				X	X			X	
Physical exam (brief)			X	X	X		X	X	X			X		
Neurological exam (complete)	X h					X				X	X		X	
Neurological exam (brief)			X	X	X		X	X	X			X		
12-lead ECG i	X h		X			X			X	X	X	X	X	
Blood pressure and pulse	X h		X	X	X	X	X	X	X	X	X	X	X	
Body weight and height	X h,j		X	X	X	X	X	X	X	X	X	X	X	

**Table 16-1: Schedule of study procedures for SP848 (Year 1)**

Study SP848	Year 1													Safety Follow-Up
	V1 b	TC c	V2	V3	V4	V5	V6	V7	V8	V9	ETV d	Unsch Visit e	Final Visit f	
Visit a														TC g
Weeks in study	0		4	8	12	20	28	36	44	52				
Clinical chemistry and hematology blood sample	X h		X			X		X		X	X			X
Endocrinology blood sample	X h,j					X				X	X			X
Blood sample for LCM PK k	X h,j		X			X		X		X	X			
Blood sample for concomitant AEDs k	X h,j		X			X		X		X	X			
Urinalysis (subjects aged 5 to 17 years)	X h,j					X				X	X			X
Pregnancy test l	X h,j,S		X U	X S			X S							
Tanner Stage m	X h,j									X		X		
Clinical GIC	X h,j					X				X	X			
Caregiver GIC	X h,j					X				X	X			
Palatability and ease of use questionnaire							X			X	X			
Dispense LCM	X		X	X	X	X	X	X	X	X	X n	X o		
LCM return/compliance			X	X	X	X	X	X	X	X	X	X o		X
Dispense diary	X		X	X	X	X	X	X	X	X	X			
Diary assessment			X	X	X	X	X	X	X	X	X	X	X	X
C-SSRS p	X h		X	X	X	X	X	X	X	X	X	X q		X
Achenbach CBCL	X					X				X	X			
Bayley-III scales	X					X				X	X			
BRIEF-P/BRIEF	X					X				X	X			
PedsQL	X					X				X	X			
AE reporting r	X h	X	X	X	X	X	X	X	X	X	X	X	X	X
Health care resource use	X		X	X	X	X	X	X	X	X	X	X	X	

AE=adverse event; AED=antiepileptic drug; C-SSRS=Columbia-Suicide Severity Rating Scale; ECG=electrocardiogram; ETV=Early Termination Visit; GIC=Global Impression of Change; LCM=lacosamide; PK=pharmacokinetics; TC=telephone contact; S=serum; SAE= serious adverse event; U=urine; Unsch=Unscheduled; V=Visit

Note: All subjects who directly enrolled into SP848 should follow the titration schedule in [Table 16-3](#).

- a A time window of  $\pm 7$  days relative to Visit 1 is applicable for all scheduled visits and telephone contacts (with the exception of the Safety Follow-Up telephone contact).
- b For subjects who have participated in SP847 (or other LCM pediatric clinical studies in epilepsy), Visit 1 is also the last visit of the primary study. At Visit 1, the informed consent will be signed (and assent, if applicable) and eligibility assessed, the medical history will be updated, body weight and height and concomitant medications including AEDs will be recorded, AEs will be assessed, and the subject diary and LCM dispensed.
- c Telephone contacts are scheduled during the following weeks during Year 1: Weeks 2, 6, 10, 16, 24, 32, 40, and 48.
- d An Early Termination Visit must be completed for all subjects who prematurely discontinue from the study.
- e If an Unscheduled Visit is needed, then the assessments noted will be performed. Additional assessments can be performed at the investigator's discretion. If the LCM dose is decreased between scheduled clinic visits due to an AE, or if a LCM dose increase is required between scheduled clinic visits, the subject must return for an Unscheduled Visit. Height will not be recorded at an Unscheduled Visit.
- f Subjects who complete the study or withdraw prematurely from the study, and who discontinue use of LCM (ie, taper), should complete the Final Visit 2 weeks after the final dose of study medication.
- g This TC occurs 28 to 35 days after the last dose of LCM.
- h For subjects enrolling from SP847 or other LCM pediatric clinical studies in epilepsy, assessments may have been done as part of the last visit of the primary study. For subjects enrolling directly into SP848, these assessments should be completed at Visit 1.
- i All subjects will be required to have a 12-lead ECG (2 interpretable recordings) conducted at LCM  $C_{max}$  1 week after an initial LCM dose increase to a LCM dose level that is  $\ge 8$ mg/kg/day or a new concomitant AED is introduced. This ECG can be conducted at an Unscheduled Visit, if necessary. Subjects having a LCM dose increase to  $\ge 8$ mg/kg/day will be required to arrive at the clinic prior to taking their morning dose of LCM. Subjects will be administered their morning LCM dose by study personnel at the clinic so that an ECG (2 interpretable recordings approximately 20 to 30 minutes apart prior to vital signs assessment) can be performed 30 minutes to 1 hour after the administration of LCM (ie, at LCM steady state  $C_{max}$ ).
- j For subjects enrolling from EP0060, these assessments should be completed at Visit 1.
- k Blood samples may be drawn at any time post-dosing with LCM.
- l For female subjects of childbearing potential, serum pregnancy tests will be performed at Visit 1, the Early Termination Visit, and the Final Visit. Urine pregnancy tests will be performed at Visits 2, 3, 4, 5, 6, 7, 8, and 9.
- m The Tanner Stage will be performed only for subjects who are pubescent at Visit 1 or who will enter puberty during the course of the study.
- n Lacosamide for taper will be dispensed only for subjects who achieve a dose of LCM  $\ge 6$ mg/kg/day (oral solution [syrup]) or  $\ge 300$ mg/day (tablet). It is recommended that the LCM dose be tapered gradually in weekly decrements of 4mg/kg/day (oral solution [syrup]) or 200mg/day (tablet). A slower taper of 2mg/kg/day (oral solution [syrup]) or 100mg/day (tablet) is permitted, if medically necessary. In case of an emergency, a faster taper is permitted after discussion with the medical monitor, whenever possible.
- o As applicable
- p For all subjects  $\ge 6$  years of age already enrolled, the "already enrolled" version should be completed at the next clinic visit, and the "since last visit" version should be completed thereafter.
- q The C-SSRS assessment should be completed if the Unscheduled Visit is due to an AE.
- r Ongoing AEs from the primary study will be followed, as well as recording of new AEs during the current study.

*Clinical Study Protocol, Section 16.1 (Table 2 Schedule of study procedures for SP848 [Year 2]). Original table:*

REDACTED COPY

This document cannot be used to support any marketing authorization application and any extensions or variations thereof.

**Table 2.** Schedule of study procedures for SP848 (Year 2)

Study SP848	Year 2								Safety Follow-Up
Visit a	V10	TC b	V11	V12	V13/TermV	ETV c	Unsch Visit d	Final Visit e	TC f
Weeks in study	60		72	84	96				
Concomitant medications	X	X	X	X	X	X	X	X	X
Concomitant AEDs	X	X	X	X	X	X	X	X	X
Physical exam (complete)					X	X		X	
Physical exam (brief)	X		X	X			X		
Neurological exam (complete)					X	X		X	
Neurological exam (brief)	X		X	X			X		
12-lead ECG g			X		X	X	X	X	
Blood pressure and pulse	X		X	X	X	X	X	X	
Body weight and height	X		X	X	X	X	X	X	
Clinical chemistry and hematology blood sample	X		X	X	X	X			X
Endocrinology blood sample				X			X		X
Blood sample for LCM PK h	X		X	X	X	X			
Blood sample for concomitant AEDs h	X		X	X	X	X			
Urinalysis (subjects aged 5 to 17 years)			X		X	X			X
Pregnancy test i	X U		X U	X U	X U	X S		X S	
Tanner Stage j					X	X			
Clinical GIC			X		X	X			
Caregiver GIC			X		X	X			
Palatability and ease of use questionnaire			X		X	X			
Dispense LCM	X		X	X	X k	X k	X l		
LCM return/compliance	X		X	X	X	X	X l	X	
Dispense diary	X		X	X	X	X			

**Table 2.** Schedule of study procedures for SP848 (Year 2)

Study SP848	Year 2								Safety Follow-Up
Visit a	V10	TC b	V11	V12	V13/TermV	ETV c	Unsch Visit d	Final Visit e	TC f
Weeks in study	60		72	84	96				
Diary assessment	X		X	X	X	X	X	X	
C-SSRS m	X		X	X	X	X	X n	X	
Achenbach CBCL			X		X	X			
Bayley-III scales			X		X	X			
BRIEF-P/BRIEF			X		X	X			
PedsQL			X		X	X			
AE reporting	X	X	X	X	X	X	X	X	X
Health care resource use	X		X	X	X	X	X	X	

AE=adverse event; AED=antiepileptic drug; C-SSRS=Columbia-Suicide Severity Rating Scale; ECG=electrocardiogram; ETV=Early Termination Visit; GIC=Global Impression of Change; LCM=lacosamide; PK=pharmacokinetics; S=serum; TC=telephone contact; TermV=Termination Visit; U=urine; Unsch=Unscheduled; V=Visit

a A time window of  $\pm 7$  days relative to Visit 1 is applicable for all scheduled visits and telephone contacts (with the exception of the Safety Follow-Up telephone contact).

b Telephone contacts are scheduled during the following weeks during Year 2: Weeks 66 and 78.

c An Early Termination Visit must be completed for all subjects who prematurely discontinue from the study.

d If an Unscheduled Visit is needed, then the assessments noted will be performed. Additional assessments can be performed at the investigator's discretion. If the LCM dose is decreased between scheduled clinic visits due to an AE, or if a LCM dose increase is required between scheduled clinic visits, the subject must return for an Unscheduled Visit. Height will not be recorded at an Unscheduled Visit.

e Subjects who complete the study or withdraw prematurely from the study, and who discontinue use of LCM (ie, taper), should complete the Final Visit 2 weeks after the final dose of study medication.

f This TC occurs 28-35 days after the last dose of LCM.

g All subjects will be required to have a 12-lead ECG (2 interpretable recordings) conducted at LCM  $C_{max}$  1 week after an initial LCM dose increase to a LCM dose level that is  $\geq 8$  mg/kg/day or a new concomitant AED is introduced. This ECG can be conducted at an Unscheduled Visit, if necessary. Subjects having a LCM dose increase to  $\geq 8$  mg/kg/day will be required to arrive at the clinic prior to taking their morning dose of LCM. Subjects will be administered their morning LCM dose by study personnel at the clinic so that an ECG (2 interpretable recordings approximately 20 to 30 minutes apart prior to vital signs assessment) can be performed 30 minutes to 1 hour after the administration of LCM (ie, at LCM steady-state  $C_{max}$ ).

h Blood samples may be drawn at any time post-dosing with LCM.

i For female subjects of childbearing potential, serum pregnancy tests will be performed at the Early Termination Visit and at the Final Visit. Urine pregnancy tests will be performed at Visits 10, 11, 12, and 13.

- j The Tanner Stage will be performed only for subjects who are pubescent at Visit 1 or who will enter puberty during the course of the study.
- k Lacosamide for taper will be dispensed only for subjects who achieve a dose of LCM  $\geq$ 6mg/kg/day (oral solution [syrup]) or  $\geq$ 300mg/day (tablet). It is recommended that the LCM dose be tapered gradually in weekly decrements of 4mg/kg/day (oral solution [syrup]) or 200mg/day (tablet). A slower taper of 2mg/kg/day (oral solution [syrup]) or 100mg/day (tablet) is permitted, if medically necessary. In case of an emergency, a faster taper is permitted after discussion with the medical monitor, whenever possible.
- l As applicable.
- m For all subjects  $\geq$ 6 years of age already enrolled, the “already enrolled” version should be completed at the next clinic visit, and the “since last visit” version should be completed thereafter.
- n The C-SSRS assessment should be completed if the Unscheduled Visit is due to an AE.

*Was revised to:*

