### MODIFICATIONS/CHANGES

- With this protocol amendment, approximately 100 eligible pediatric subjects  $\geq 4$  years to  $\leq 17$  years of age with partial-onset seizures (deemed appropriate for treatment with adjunctive LCM) who have not previously participated in a LCM clinical study will be permitted to enroll directly into SP848. Therefore, the study title has been updated to reflect that SP848 is no longer exclusively an “extension study.”
- Study contact information has been updated (eg, Clinical Program Director, Safety Physician, and SAE reporting).
- Information was added to Section 1 (Summary) and throughout the protocol to indicate that approximately 100 eligible pediatric subjects  $\geq 4$  years to  $\leq 17$  years of age with partial-onset seizures (deemed appropriate for treatment with adjunctive LCM) who have not previously participated in a LCM clinical study will be permitted to enroll directly into SP848. A Screening and Titration Visits have been added for subjects enrolling directly into SP848.
- Information was added to Section 1 (Summary) and throughout the protocol to reflect the addition of the Achenbach CBCL, Bayley-III scales, and a LCM palatability and ease of use questionnaire as assessments in SP848.
- Modifications were made to Section 4.3.1 (Inclusion criteria) and Section 4.3.2 (Exclusion criteria) in order to address subjects who have participated in SP847 or other LCM pediatric clinical studies in epilepsy or who have enrolled directly into SP848 without previous participation in a LCM clinical study.
- Information was added to Section 8.4.4 (12-lead ECG) and throughout the protocol to clarify that all subjects will be required to have a 12-lead ECG (2 interpretable recordings approximately 20 to 30 minutes apart) conducted at LCM Cmax 1 week after an initial LCM dose increase to a LCM dose that is  $\geq 8$ mg/kg/day or when a new concomitant AED is introduced.

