All subjects will be required to have an ECG (2 interpretable recordings) conducted at LCM  $C_{max}$  1 week after an initial LCM dose increase. This ECG can be conducted at an Unscheduled Visit, if necessary. These subjects will be required to arrive at the clinic prior to taking their morning dose of LCM. Subjects will be administered their morning LCM dose by study personnel at the clinic so that an ECG (2 interpretable recordings approximately 20 to 30 minutes apart prior to vital signs assessment) can be performed 30 minutes to 1 hour after the administration of LCM (ie, at LCM steady state  $C_{max}$ ).

*Was revised as follows:*

- A 12-lead ECG (2 interpretable recordings) is also required when the dose of LCM is increased to a LCM dose level that is  $\geq 8\text{mg/kg/day}$  or a new concomitant AED is introduced. The ECG should be performed after the increased dose of LCM or the new AED has reached steady-state. This ECG can be done at the next scheduled visit. When the ECG assessment is done, 2 interpretable recordings will be performed approximately 20 to 30 minutes apart prior to vital sign assessment and collection of blood samples (if applicable), but 30 minutes to 1 hour after the administration of LCM (if applicable).

All subjects will be required to have an ECG (2 interpretable recordings) conducted at LCM  $C_{max}$  1 week after an initial LCM dose increase to a LCM dose level that is  $\geq 8\text{mg/kg/day}$ . This ECG can be conducted at an Unscheduled Visit, if necessary. These subjects will be required to arrive at the clinic prior to taking their morning dose of LCM. Subjects will be administered their morning LCM dose by study personnel at the clinic so that an ECG (2 interpretable recordings approximately 20 to 30 minutes apart prior to vital signs assessment) can be performed 30 minutes to 1 hour after the administration of LCM (ie, at LCM steady state  $C_{max}$ ).

*Clinical Study Protocol, Section 5.6 (Visit 3 [Week 8]), final 2 paragraphs. Original text:*

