if necessary. These subjects will be required to arrive at the clinic prior to taking their morning dose of LCM. Subjects will be administered their morning LCM dose by study personnel at the clinic so that an ECG (2 interpretable recordings approximately 20 to 30 minutes apart prior to vital signs assessment) can be performed 30 minutes to 1 hour after the administration of LCM (ie, at LCM steady state  $C_{max}$ ).

*Was revised as follows:*

An Unscheduled Visit may be performed at the investigator's discretion. If the LCM dose is decreased between scheduled clinic visits due to an AE, if an LCM dose increase is required at any time, or if a new concomitant AED is introduced, the subject must return for an Unscheduled Visit. If an AE prompts a dose reduction, the reduction can be implemented immediately at the investigator's discretion. However, the subject should return to the clinic as soon as possible for an Unscheduled Visit.

The following assessments are required:

- Concomitant medications assessment
- Concomitant AEDs assessment
- Brief physical examination
- Brief neurological examination
- 12-lead ECG (2 interpretable recordings approximately 20 to 30 minutes apart prior to vital signs assessment and collection of any blood samples)
- Vital signs assessment (blood pressure and pulse)
- Body weight
- LCM return/compliance (as applicable)
- Subject diary assessment
- C-SSRS (only if Unscheduled Visit is conducted due to an AE)
- Adverse event reporting
- Dispense LCM (as applicable)

Additional assessments can be performed at the investigator's discretion.

All subjects will be required to have an ECG (2 interpretable recordings) conducted at LCM  $C_{max}$  1 week after an initial LCM dose increase to a LCM dose level that is  $\geq 8\text{mg/kg/day}$  or after a new concomitant AED is introduced. This ECG can be conducted at an Unscheduled Visit, if necessary. Subjects having a LCM dose increase to  $\geq 8\text{mg/kg/day}$  will be required to arrive at the clinic prior to taking their morning dose of LCM. Subjects will be administered their morning LCM dose by study personnel at the clinic so that an ECG (2 interpretable recordings approximately 20 to 30 minutes apart prior to vital signs assessment) can be performed 30 minutes to 1 hour after the administration of LCM (ie, at LCM steady state  $C_{max}$ ).

*Clinical Study Protocol, Section 5.19 (Final Visit). Original text:*

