All subjects will be required to have a 12-lead ECG (2 interpretable recordings approximately 20 to 30 minutes apart) conducted at LCM  $C_{max}$  1 week after an initial LCM dose increase or when a new concomitant AED is introduced. This ECG can be conducted at an Unscheduled Visit, if necessary. Subjects having a LCM dose increase to  $\geq 8\text{mg/kg/day}$  will be required to arrive at the clinic prior to taking their morning dose of LCM. Subjects will be administered their morning LCM dose by study personnel at the clinic so that an ECG (2 interpretable recordings approximately 20 to 30 minutes apart prior to vital signs assessment) can be performed 30 minutes to 1 hour after the administration of LCM (ie, at LCM steady state  $C_{max}$ ).

*Clinical Study Protocol, Section 8.4.7 (Achenbach CBCL) was newly added as follows and subsequent section numbers were adjusted accordingly:*

The Achenbach CBCL is a widely used validated questionnaire to evaluate a child's competencies and behavioral/emotional problems. Behavioral problems will be scored by the parent(s)/legal representative(s). Depending on the subject's age, 2 versions of the CBCL will be used. The CBCL/1½-5 checklist is intended for use in children 18 months to 5 years and 11 months of age. For subjects  $\geq 6$  years to  $\leq 17$  years of age, the CBCL/6-18 version will be used.

The same scale will be completed at the Screening Visit (subjects enrolling directly into SP848), Visit 1 (subjects enrolling from SP847 or other pediatric clinical studies in epilepsy), and Visit 13/Termination Visit (or Early Termination Visit) (all subjects) by the parent(s)/legal representative(s). The completion of the Achenbach CBCL will require approximately 45 minutes.

In both questionnaires, the occurrence of certain problems and behaviors in the past 6 months will be scored on the following scale:

- 0=not true (as far as known)
- 1=somewhat or sometimes true
- 2=very true or often true

Eight syndrome scores will be calculated from these questions, which will in turn be summarized by 2 composite scores. Additionally, for each score on the question, syndrome, and total level, categorizations based on a normative sample will be used to evaluate normal, borderline, or clinically relevant behavior.

In addition, the Achenbach CBCL/6-18 includes ratings related to performance in school, activities in leisure time, and special interests.

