		Titration Visit 1	Titration Visit 2	Titration Visit 3	Titration Visit 4	Titration Visit 5	Titration Visit 6
Visit	Screening Visit						
Bayley-III scales	X						
BRIEF-P/BRIEF	X						
PedsQL	X						
AE reporting	X	X	X	X	X	X	X
Health care resource use	X	X	X	X	X	X	X

AE=adverse event; AEDs=antiepileptic drugs;  $C_{\max}$ =maximum plasma concentration; C-SSRS=Columbia-Suicide Severity Rating Scale;

ECG=electrocardiogram; GIC=Global Impression of Change; LCM=lacosamide

a All subjects will be required to have a 12-lead ECG (2 interpretable recordings) conducted at LCM  $C_{\max}$  1 week after an initial LCM dose increase to a LCM dose level that is  $\geq 8\text{mg/kg/day}$  or a new concomitant AED is introduced. This ECG can be conducted at an Unscheduled Visit, if necessary. Subjects having a LCM dose increase to  $\geq 8\text{mg/kg/day}$  will be required to arrive at the clinic prior to taking their morning dose of LCM. Subjects will be administered their morning LCM dose by study personnel at the clinic so that an ECG (2 interpretable recordings approximately 20 to 30 minutes apart prior to vital signs assessment) can be performed 30 minutes to 1 hour after the administration of LCM (ie, at LCM steady state  $C_{\max}$ ).

b For female subjects of childbearing potential, serum pregnancy tests will be performed at the Screening Visit.

c For all subjects  $\geq 6$  years of age already enrolled, the “already enrolled” version should be completed at the next clinic visit, and the “since last visit” version should be completed thereafter.

*Clinical Study Protocol, Section 16.3 (Declaration and signatures of person responsible for the study). The signature block for the Clinical Project Manager was updated as follows:*

Clinical Project Manager

[REDACTED], RN, MSN

\_\_\_\_\_  
Date / Signature

REDACTED COPY

This document cannot be used to support any marketing authorization application and any extensions or variations thereof.

## 17.6 PROTOCOL AMENDMENT 6

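### The dose trigger for the witnessed-dose Cmax ECG is set in mg/kg/day only, so under the 600 mg/day cap it cannot be met above 75 kg; the gap lies mainly after Visit 1, and Sections 8.4.4 and 5.2 answer differently

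*Protocol*

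**What the plan says.** **Threshold rule.** Table 16-1 footnote i (Amendment 6 text) addresses all subjects. It calls for two interpretable recordings at Cmax one week after an initial increase to at least 8 mg/kg/day, or when a new antiepileptic drug (AED) is introduced. Subjects with an increase to at least 8 "mg/kg/day will be required to arrive at the clinic prior to taking their morning dose of LCM"; site staff then give the dose and the ECG follows 30 to 60 minutes later. Table 16-2 footnote g and Section 5.18 say the same, as does Table 3 footnote a (Titration Visits), where such subjects "will be required to arrive at the clinic prior to taking their morning dose of LCM". Sections 5.5, 5.6 and 5.8 place the Cmax ECG "1 week after an initial LCM dose increase to a LCM dose level that is" at least 8 mg/kg/day. They add a steady-state ECG, possible at the next scheduled visit, with the same threshold: "A 12-lead ECG (2 interpretable recordings) is also required when the dose of LCM is increased to a LCM dose level that is" at least 8 mg/kg/day, or when a new AED is introduced.

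**Dose limit.** Section 4.1.1 caps the dose at 12 mg/kg/day or 600 mg/day, whichever is lower, and allows increases only at office visits.

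**Places that differ.**
- Section 8.4.4, as revised by Amendment 4, puts the Cmax ECG "1 week after an initial LCM dose increase or when a new concomitant AED is introduced", with no dose threshold. It keeps 8 mg/kg/day for arriving undosed.
- Section 5.2 (Titration Visits) prints the trigger as 8 mg/day and attaches no weight-based condition to arriving undosed.
- On when an Unscheduled Visit is required, Section 5.18 says "if an LCM dose increase is required at any time, or if a new concomitant AED is introduced". Table 16-1 footnote e is narrower: "if a LCM dose increase is required between scheduled clinic visits, the subject must return for an Unscheduled Visit".

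**The concern.** A weight-based trigger combined with an absolute dose cap stops working above some body weight. Here that weight is within reach of an adolescent, and the subjects who drop out of the rule can be taking the highest dose the study allows. The rule is nevertheless written for all subjects. The taper footnote in the same table gives both a mg/kg/day and a mg/day figure; the ECG footnote gives only the first.

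QTc of 500 ms or more and second- or third-degree AV block are mandatory withdrawal criteria (Section 4.3.3), and serious arrhythmias including AV block are adverse events of special interest (Section 8.2.2). The witnessed dose secures the timing of the recording near peak concentration. The rationale for this ECG is not in the part of the protocol at hand, so its purpose is inferred from these criteria.

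**Working it through.** **Inputs.** Trigger 8 mg/kg/day (Table 16-1 footnote i). Cap: the lower of 12 mg/kg/day and 600 mg/day (Section 4.1.1). Adult-to-child conversion and titration table (Sections 4.4.1.2 and 4.4.1.3, Amendment 4 text). ECG visits from Section 5.

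**1. The plan's own figure.** (600/70) x 1.4 = 12.0 mg/kg/day, which reproduces the stated conversion of the adult dose. The cap binds above 600/12 = 50 kg.

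**2. Weight at which the trigger becomes unreachable.** The highest permitted dose at weight w is min(12, 600/w) mg/kg/day. It reaches 8 only if w <= 600/8 = 75 kg.

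| Weight (kg) | Highest permitted dose (mg/kg/day) | Trigger reachable |
|---|---|---|
| 70 | 8.57 | yes |
| 75 | 8.00 | yes |
| 76 | 7.89 | no |
| 80 | 7.50 | no |
| 100 | 6.00 | no |

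By tablet step, 400 mg/day triggers at 50 kg or less (400/8), 500 mg/day at 62.5 kg or less and 600 mg/day at 75 kg or less.

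**3. Could this be an intended exemption for low exposure?** On the protocol's own scale, 8 mg/kg/day corresponds to (8/1.4) x 70 = 400 mg/day, the tablet step beside 8 mg/kg/day in the titration table. A subject above 75 kg on 600 mg/day is well past that, and at 600/400 = 1.5 times the top of the approved 200 to 400 mg/day range in Section 2.

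**4. Worst-case wait.** Scheduled ECGs fall at Weeks 0, 4, 28, 52, 72 and 96. The steady-state rule carries the same threshold, so it adds nothing above 75 kg after a dose increase. An ECG at the visit where the dose is raised can precede the new dose, so the next scheduled ECG is the one that counts.

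| Increase at Week | 4 | 8 | 12 | 20 | 28 | 36 | 44 | 52 | 60 | 72 | 84 |
|---|---|---|---|---|---|---|---|---|---|---|---|
| Next scheduled ECG | 28 | 28 | 28 | 28 | 52 | 52 | 52 | 72 | 72 | 96 | 96 |
| Wait (weeks) | 24 | 20 | 16 | 8 | 24 | 16 | 8 | 20 | 12 | 24 | 12 |

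A 75 kg subject raised to 600 mg/day has the Cmax ECG after 1 week. These waits apply only if the footnotes govern and no Unscheduled Visit follows the increase. If 8.4.4 governs and the increase is the subject's initial one, the wait is 1 week at any weight.

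**5. The proposed trigger**, dose >= min(8w, 600) mg/day. For w <= 75, 8w <= 600, so the footnote trigger is unchanged. Above 75 kg, tablets trigger at 600 mg/day (Week 6 of titration). Oral solution triggers at the Week 4 step for 76, 80 and 90 kg (8 mg/kg/day, capped at 600 mg/day) and at the Week 3 step for 100 kg (6 x 100 = 600 mg/day).

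**The case against.** The strongest reply is that much of this is covered elsewhere.

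- Section 8.4.4, the dedicated ECG section, gives every subject a Cmax ECG after an initial increase.
- Section 5.18, read literally, brings the subject back after any increase, and an ECG is required at that visit.
- Direct enrollers have an ECG at each Titration Visit and then a post-dose-timed one at Visit 1, at least 5 days after the last Titration Visit. A heavy subject titrated to 600 mg/day therefore has a peak-timed ECG planned.
- Section 5.2, read literally, triggers at every titration step.
- A new AED still triggers a Cmax ECG.

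Most of this stands, and it confines the point mainly to increases after Visit 1. It does not remove it. The first increase under 8.4.4 need not be the one to 600 mg/day, and 8.4.4 still ties undosed arrival to 8 mg/kg/day. The routine ECG in 5.18 is not timed to the new dose, and footnote e is narrower than 5.18. The figure in 5.2 reads as a unit slip, because Table 3 footnote a gives mg/kg/day for the same visits.

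A second reply is that a weight-based threshold may be deliberate. The protocol's own conversion tells against that, though it cannot settle intent.

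A reader might infer that subjects above 75 kg have no ECG monitoring, or that they will typically wait 8 to 24 weeks. The documents support neither: other ECGs remain, and the waits are a worst case.

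**Conclusion.** The point holds as a gap in wording with a limited safety consequence. Under the footnotes and Sections 5.5, 5.6, 5.8 and 5.18, no permitted dose increase triggers the witnessed-dose Cmax ECG above 75 kg. Sections 8.4.4 and 5.2 give different answers for the same subjects, so sites cannot tell which rule applies. What is lost is mainly that ECG after increases following Visit 1, with a wait of up to 24 weeks to the next scheduled ECG only if the footnotes govern.

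The number of subjects above 75 kg is not stated. Entry is allowed up to 18 years and the eligibility criteria shown set no upper weight limit, so the point concerns heavy adolescents and probably few of them.

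The conclusion assumes that the latest revised wording shown is still in force. Amendment 8 lists changes only to footnotes f and g of Table 16-1 and e and f of Table 16-2, which supports this for the footnotes. The current Section 5 and 8.4.4 text is in the part not at hand.

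**What to change.** In Table 16-1 footnote i, Table 16-2 footnote g, Table 3 footnote a and Sections 5.2, 5.5, 5.6, 5.8 and 5.18, set the dose trigger for the Cmax ECG and for arriving undosed as: *an initial increase to >=8 mg/kg/day or to 600 mg/day, whichever is the lower dose*. Keep the new-AED trigger. Apply the same wording to the steady-state ECG sentence in 5.5, 5.6 and 5.8, and correct the unit in 5.2.

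In Section 8.4.4 change only the undosed-arrival sentence, and leave its call for an ECG after an initial increase in place. The Amendment 4 change list describes that section with a threshold, "conducted at LCM Cmax 1 week after an initial LCM dose increase to a LCM dose that is" at least 8 mg/kg/day. Narrowing 8.4.4 to match would remove monitoring at every weight, and this point gives no reason to do that.

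A 400 mg/day alternative should not replace the proposed trigger. Because the rule fires on the initial increase, a 60 kg subject would be checked at 400/60 = 6.67 mg/kg/day and not again at 500 mg/day (8.33 mg/kg/day). If the clinical team wants a check at 400 mg/day, it should be an additional ECG.

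The cost is a wording change and one timed ECG, possibly at an Unscheduled Visit, for each subject above 75 kg raised to 600 mg/day. The footnote trigger is unchanged at 75 kg or below.
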